11.4. Laboratory Evaluations

Blood samples for chemistry, hematology and lipid testing and urine samples will be collected based on the collection schedule provided in the Schedule of Assessments in [Section 3.7](#) . A list of the clinical laboratory tests that will be performed can be found in Appendix 16.2 of the protocol. A central laboratory will be used to analyze the clinical laboratory samples.

If laboratory values were considered clinically significant by the investigator, the value was to be reported as a TEAE, and thus clinically significant lab values are reported accordingly in the adverse events.

Summary tables will include descriptive statistics for the actual values and changes from baseline by scheduled time point in hematology, chemistry, lipid testing, and quantitative urinalysis test results by treatment group. For qualitative urinalysis parameters, frequency counts and percentages will be presented over time for these categorical data by treatment.

A shift table based on reported lab values classified as low/normal/high will be created for each lab parameter to assess shift from baseline to each subsequent visit. Similarly, a shift table comparing baseline lab value classification to shifts occurring anytime following initial dose by highest classification and lowest clarification will be provided.

All parameters will be converted to consistent units according to the Standard International System of Units (SI) before summarization.

All clinical laboratory results will be listed by site, subject and timing of collection. Out-of-range values will be flagged as low or high where applicable based on lab normal ranges provided by the lab(s). Listings of abnormal hematology and chemistry test results will be provided.

All clinical laboratory parameters will be plotted over time (with mean and SD) by study visit.

This document is confidential.

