BPN14770 has cognitive benefit in the mouse Novel Object Recognition (NOR) test at ≥ 0.3 mg/kg by PO, as shown by an increase in the Discrimination Index. BPN14770 maximum plasma concentration (C_{max}) at the minimum effective dose (MED) was 160 ng/mL (in plasma) and 40 ng/gm (in brain). Cognitive benefit is maintained after chronic dosing for 7 days. BPN14770 also has benefit in a mouse model of cholinergic impairment, the scopolamine-impaired Y-maze (male C57Bl6 mice MED = 1 mg/kg).

BPN14770 did not affect cardiovascular function in beagle dogs at doses up to 100 mg/kg, nor did the compound affect respiratory function or exert neuropharmacologic effects in rats at doses up to 60 mg/kg. In the in vitro human Ether-à-go-go-Related Gene (hERG) assay, an increase in current of 12% and 33% was seen at concentrations of 10 and 30 μ M, respectively. No IC_{50} could be calculated due to this minor increase in current.

In rat toxicology studies of 28-days and 13-weeks, BPN14770 was well tolerated up to 60 mg/kg with no deaths on study, and no adverse hematology, clinical chemistry, liver weight or gross necropsy findings. There were no microscopic findings. Unlike the PDE4 inhibitors roflumilast and apremilast, BPN14770 did not cause mesenteric vasculopathy at the doses studied.

In dog toxicology studies of 28-days and 13-weeks, the no observed adverse effect level (NOAEL) for BPN14770 was 30 mg/kg. At 100 mg/kg in the 28-day study, BPN14770 caused inappetance and weight loss and in female dogs an approximately 30 msec increase in QTc with a concomitant increase in heart rate of 10 bpm. There were no changes in hematology or ophthalmology. Macroscopic observations included pale livers in two of eight animals at 100 mg/kg which correlated with mild alanine transaminase (ALT) elevation only in those two animals. Microscopic changes of periportal hepatocellular cytoplasmic vacuolation were observed in the livers of one male and two female dogs at 100 mg/kg. No liver changes were observed in recovery dogs suggesting that these changes, if present, were reversible.

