Among the elderly subject cohorts, the percentage of subjects who experienced at least one treatment-emergent adverse event was similar between the 10-mg BID, 20-mg BID, and placebo groups (ranging from 30% to 50%) and was higher for the 40-mg BID dose group (90%). Likewise, the percentage of subjects with at least one drug-related adverse event was also higher for the 40-mg BID dose group (70%) compared with the 10-mg BID dose group (40%), the 20-mg BID dose group (20%), and the placebo group (26.7%). Adverse events reported in 2 or more elderly subjects within a dose group were all reported by subjects in the 40-mg dose group and consisted of diarrhea, increased alanine and aspartate aminotransferase, hot flush (each reported at a frequency rate of 20%) and headache (reported at a frequency rate of 40%). Across the elderly subject cohorts, 2 adverse events (dizziness and hypotension) of moderate severity were reported in 1 of the 10 subjects (10.0%) in the 10 mg BID dose group, and 1 headache of moderate severity was reported in 1 of 10 subjects (10.0%) in the 40-mg BID dose group. Among the elderly subject dose groups, no clinically significant effects of multiple oral doses of BPN14770 (10 mg, 20 mg, or 40 mg) were observed on biochemistry, hematology, or urinalysis; vital signs; or ECGs.

With respect to cognitive testing, BPN14770 10 mg given twice daily was associated with improvement in complex attention/working memory and delayed recall of both visual and verbal information. Treatment with BPN14770 20 mg twice daily was associated with similar benefits as the 10 mg twice daily regimen, excluding improvement in delayed recall of visual information. Neither the 10- or 20-mg BID regimens was associated with improvement in psychomotor function, visual, or verbal learning, or executive function. The 40-mg BID regimen was not associated with improvement in any cognitive domain.

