6.3 Subject Exclusion Criteria

The following Exclusions apply to findings during Screening or at Baseline (Day 1):

1. Any medical or neurological condition (other than early stage AD) that might be a contributing cause to the subject's cognitive impairment, including prominent features of

- Lewy body dementia, behavioral variant frontotemporal dementia, semantic variant primary progressive aphasia or nonfluent/agrammatic variant primary progressive aphasia.
2. No substantial concomitant cerebrovascular disease, defined by a history of stroke temporally related to the onset or worsening of cognitive impairment; or the presence of multiple or extensive infarcts or severe white matter hyperintensity burden on imaging.
 3. No evidence for another concurrent, active neurological disease, or a non-neurologic medical co-morbidity or use of medication that could have a substantial effect on cognition.
 4. Clinically significant major psychiatric illness during the past 6 months, as determined by the Investigator.
 5. History of unstable angina, myocardial infarction, chronic heart failure, or clinically significant conduction abnormalities during the past year.
 6. Clinically significant liver or renal disease, defined as creatinine clearance <30 mL/min at screening.
 7. Clinically significant abnormality, in the Investigator's judgment, in hematology, chemistry, or urinalysis.
 8. Positive serology results for hepatitis B surface antigen (HbsAg) or hepatitis C virus (HCV). HCV subjects who have been treated and are now RNA negative are eligible to participate.
 9. Abnormal liver function test at the Screening Visit (aspartate aminotransferase or alanine aminotransferase $>2 \times$ the upper limit of normal [ULN], or total bilirubin $>1.7 \times$ ULN, based on appropriate age and gender normal values). Subjects with Gilbert's syndrome are eligible to participate despite elevated bilirubin. . Subjects may be re-screened for these tests once.
 10. Marked hypotension (systolic blood pressure [BP] <90 mmHg or diastolic BP <50 mmHg) or hypertension (systolic BP >160 mmHg or diastolic BP >100 mmHg) based on sitting values. Out-of-range results may be repeated once at Screening and at Baseline, if needed. Eligibility must be confirmed at Baseline.

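### The laboratory shift tables in SAP 11.4 do not show how far ALT, AST or bilirubin rises above ULN, and no planned table counts subjects by size of rise

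*SAP*

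**What the plan says.** SAP 11.4 (Laboratory Evaluations) gives the main categorical display: "A shift table based on reported lab values classified as low/normal/high will be created for each lab parameter", comparing baseline with each later visit. A second table uses the same classes for "shifts occurring anytime following initial dose by highest classification and lowest" class. The section also plans descriptive statistics for values and changes from baseline by scheduled visit, mean and SD plots, a full listing with low or high flags, and a listing of abnormal hematology and chemistry results. SAP 6.1 includes minimum and maximum in the descriptive statistics. It also keeps unscheduled and repeat assessments out of summary tables.

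Protocol 6.3, Exclusion 9, applies to an "Abnormal liver function test at the Screening Visit (aspartate aminotransferase or alanine aminotransferase" result above 2 x ULN, or total bilirubin above 1.7 x ULN, with Gilbert's syndrome exempt for bilirubin. Exclusion 7 separately removes chemistry abnormalities that the investigator judges clinically significant.

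On earlier liver findings, Protocol 4.3.2.2 reports, for the elderly 40 mg BID group, "increased alanine and aspartate aminotransferase, hot flush (each reported at a frequency rate of 20" percent). The same section states that in elderly subjects "no clinically significant effects of multiple oral doses of BPN14770 (10 mg, 20 mg, or 40 mg) were observed on biochemistry". Protocol 4.3.1 describes, in dogs at 100 mg/kg, "mild alanine transaminase (ALT) elevation only in those two animals".

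For comparison, SAP 11.6 counts subjects in four QTcF bands, by visit and by highest value during double-blind treatment.

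**The concern.** A three-class table records whether a result crossed ULN. For transaminases, the useful question is how far above ULN a subject went, how many subjects in each arm did so, and whether bilirubin rose at the same time. The planned shift tables answer none of these. They are also uninformative for subjects who start above ULN.

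There is a documented reason to look. Raised transaminases were reported as adverse events after 8 days of dosing at 40 mg BID. This trial uses lower doses but treats to Day 91. At stake is whether a reader of the summary tables could tell an arm with a few marginal elevations from an arm with the same number of large ones. The SAP applies graded bands to QTcF, so the method is already within its plan.

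**Working it through.** The plan states no figure for this point, so there is none to reproduce. The check applies the SAP's classification rule to example values and then asks what the other outputs add.

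**1. The rule applied.** Let x be ALT divided by ULN, with x > 1 classed as high.

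| Baseline x | Post-dose x | Shift-table cell |
|---|---|---|
| 0.8 | 2.1, 3.1, 5.1, 10.1 or 20.1 | normal to high, all 5 |
| 1.2 | same five values | high to high, all 5 |
| 1.9 | same five values | high to high, all 5 |
| 2.0 | same five values | high to high, all 5 |

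All 3 x 5 = 15 combinations with a baseline above ULN fall in the same cell, and so do all five with a normal baseline. The any-time table uses the same classes, so its highest class is also just high.

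**2. Effect on an arm comparison (assumed numbers, to show the mechanism only).** Suppose 8 of 85 subjects per arm, all with normal baselines, have a high post-dose ALT. On placebo all 8 are at or below 1.5 x ULN; on 25 mg, 4 of the 8 exceed 5 x ULN. The shift table reads 8 against 8. A count above 5 x ULN reads 0 against 4.

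**3. What the by-visit statistics add.**
- *Mean.* One subject going from 2.0 to 10.1 x ULN in an arm of 80 moves the mean change by (10.1 − 2.0)/80 = 8.1/80 = 0.10 x ULN, which is easily overlooked.
- *SD.* If n − k subjects have SD s, and k subjects all sit a distance d from the others' mean, then SD² = [(n − k − 1)s² + (k(n − k)/n)d²]/(n − 1). Assume mean 0.6 and s = 0.25, in x ULN, with n = 85.
  - One subject at 5.5 (d = 4.9): (83 x 0.0625 + (84/85) x 24.01)/84 = 0.344, so SD = 0.59.
  - Four at 5.5 at the same visit: (80 x 0.0625 + (4 x 81/85) x 24.01)/84 = 1.149, so SD = 1.07.
  - For the change in the 80-subject example (s = 0.25, other subjects' mean change 0, d = 8.1): (78 x 0.0625 + (79/80) x 65.61)/79 = 0.882, so SD = 0.94.
- *Maximum.* It shows the largest scheduled value at each visit, without that subject's baseline or the number of subjects affected.

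The SD and maximum would therefore alert a careful reader to large outliers at scheduled visits. They do not supply a count of subjects, and a peak found only on an unscheduled or repeat draw is absent from them under SAP 6.1.

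**4. What the adverse event tables add.** SAP 11.3 gives number and percentage of subjects by preferred term and maximum severity, by arm. Entry depends on the investigator calling the value clinically significant (SAP 11.4). Protocol 9.1 does not require reporting of a result unconfirmed by repeat testing, and Protocol 8.9 leaves the repeat to the investigator. Protocol 9.3.2 grades severity by interference with daily activities, so a large rise without symptoms can be graded mild. These tables count reported events; they do not measure size.

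**5. What the listings add.** Every value is there, flagged low or high. A reader could build the missing count by hand, but no by-arm summary is prespecified.

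**The case against.** Much of the case on the other side stands and sets the scale of this point.

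- A reader might infer that the documents name liver injury as a risk of this drug. They do not. The human finding is 20% (2 of 10) at 40 mg BID, with no clinically significant biochemistry effect stated. The dog ALT rise was mild, in two of eight animals at 100 mg/kg against a no-adverse-effect level of 30 mg/kg, and no liver changes were seen in recovery animals.
- A reader might infer that everyone between 1 and 2 x ULN enters with a high baseline. Exclusion 7 can remove some of them. Exclusion 9 applies at Screening, whereas SAP 6.2 expects baseline to be the Day 1 value. The number affected is unknown.
- A reader might infer that size is lost altogether. It is not: SD, maximum, change from baseline and listings show part of it, as step 3 confirms.
- Adverse event reporting is a partial safeguard. Treatment-emergent events include worsening of those present at baseline, Protocol 9.1 requires follow-up of clinically significant values, and Protocol 11.5 adds Fisher's exact test against placebo for each event.
- A reader might infer that the Phase 3 dose choice rests on these tables. SAP 3.1 says only that the study outcomes inform it, and SAP 8.3 discusses efficacy endpoints.
- The DSMB charter may call for liver displays. It was not available, so this is open.

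What the objection does not supply is any planned output that counts subjects by arm and by size of rise, or that pairs ALT with bilirubin.

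**Conclusion.** The point holds as a reporting gap. For ALT, AST and bilirubin, both planned shift tables carry no information on size above ULN, and a subject with a baseline above ULN can show no upward shift. This follows directly from the classification rule and needs no assumption. How often it would matter cannot be derived from the documents: the 8 against 8 example and the SD figures rest on assumed values. Other outputs reveal large scheduled values in part, but the by-arm count by size and the joint ALT and bilirubin view are missing from the SAP. Sample size, power, alpha and the primary analysis are unaffected. The change is a worthwhile, inexpensive improvement, and its absence does not invalidate the safety analysis.

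**What to change.** In SAP 11.4 add:

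1. By arm, the number (%) of subjects by highest post-dose ALT, AST and total bilirubin in prespecified multiples of ULN, cross-tabulated against baseline category in the same units. Possible display bands are >1–2, >2–3, >3–5, >5–10 and >10 for ALT and AST, and >1–1.7, >1.7–2 and >2 for bilirubin. Only 2 and 1.7 come from the documents (the entry limits); the sponsor should set the rest before unblinding. These are tabulation bands, not clinical rules.
2. A statement that unscheduled and repeat values count toward the highest value, as an exception to SAP 6.1.
3. A plot or listing of peak ALT or AST against peak total bilirubin, by arm.

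This follows the approach SAP 11.6 takes for QTcF. The low/normal/high tables can stay for the other analytes. The cost is a few extra displays from results already collected with normal ranges. Many cells will be sparse, so they should be read descriptively, without tests.

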11.5. Vital Signs

Vital signs (pulse rate, blood pressure, respiration rate, and temperature) will be measured at Screening, during the Treatment Visits, and Follow-Up as specified in the Schedule of Assessments. Blood pressure at the Screening Visit should be obtained in both arms and the arm with the higher value should be used for ongoing monitoring throughout the rest of the study. For each subject, measurement on the same arm (right or left) using the same method (either automated or manual) should occur throughout the study.

Summary table of actual values and changes from baseline by visit for each vital sign parameter will be provided by treatment groups.

All vital signs measurement data will be listed by subject and time of measurement. Weight collected at Day 1 and Week 13 will be listed with vital signs.

All vital sign parameters will be plotted over time (with mean and SD) by study visit.

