4.3.2.2 BPN14770-CNS-102

In the multiple ascending dose (MAD) trial (BPN14770-CNS-102), 76 healthy young and elderly subjects were administered multiple doses of BPN14770 twice daily (every 12 hours) for 8 days. Young subjects (≤ 45 years; $n=18$ treated, 7 placebo) received twice-daily doses of 15 mg, 30 mg, 50 mg or placebo for 8 days. Elderly subjects (≥ 60 years; $n=30$ treated, 15 placebo) received twice-daily doses of 10 mg, 20 mg, and 40 mg for 8 days. Twice-daily dosing was selected to ensure adequate BPN14770 levels in the brain and plasma throughout the day and night. An additional cohort of 6 young subjects received a once-daily dose of 75 mg for 8 days to obtain additional safety and pharmacokinetic (PK) data at a dose level close to the MTD determined in the SAD study.

No deaths or serious adverse events were reported, and no subjects in either the young or elderly cohorts withdrew from the study due to adverse events. All treatment-emergent adverse events resolved without sequelae by the follow-up visit.

All study-drug related adverse events that occurred in more than 1 young subject were in the 75-mg QD dose group and consisted of nausea (reported by 4 of 6 subjects, vomiting (reported by 2 of 6 subjects who also experienced nausea), and decreased appetite (reported by 3 of 6 subjects). Across the young subject cohorts, all but 2 of the reported adverse events were mild in severity; moderate nausea and vomiting were reported in 1 of 6 subjects (16.7%) in the 75-mg QD dose

group on Day 2 of multiple dosing. These events were considered by the Investigator as probably related to study treatment, resolved without sequelae within 13 hours of onset, and did not recur upon subsequent dosing. Among the young subject dose groups, no clinically significant effects of multiple oral doses of BPN14770 (15 mg, 30 mg, 50 mg, or 75 mg) were observed on biochemistry, hematology, or urinalysis; vital signs; or ECGs.

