8.5 Height, Weight, Body Mass Index

Body weight and height are to be measured at Screening, and body weight will be repeated at Baseline and the Week 13 visit as specified in the Schedule of Assessments. Subjects will wear indoor clothing and remove their shoes prior to the measurements. Body Mass Index (BMI) will be calculated and recorded.

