11.6. ECG

Single 12-lead ECGs will be performed at clinic visits as specified in [Table 2](#) Schedule of Assessments.

Summary tables by visit and change from baseline to visit for each ECG parameter (Heart Rate, PR interval, QRS interval, QT interval, RR interval, and QTc interval) will be provided.

The overall results of the ECGs recorded as “normal”, “abnormal, not clinically significant (NCS)” or “abnormal, clinically significant (CS)” will be summarized by treatment group at each visit.

12-lead ECG data will be listed by subject and visit.

The ECG analysis will include a careful review of QTcF values. As part of this review, a summary of the number (percent) of subjects with QTcF values (at pre-treatment and then at any time post-first dose) in the following ranges will be provided: ≤ 450 msec, >450 to ≤ 480 msec, >480 to ≤ 500 msec, and >500 msec. This will be performed by visit as well as at ANY time during the double-blind treatment period (where the highest QTcF value will be used for that assessment).

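### Body weight is only listed, so weight change is never summarised by arm; a minor companion gap is that no table counts subjects by size of QTcF increase

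*SAP*

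**What the plan says.** **Collection.** Protocol 8.5 measures weight at Screening and states that "body weight will be repeated at Baseline and the Week 13 visit as specified in the Schedule of Assessments". Protocol 10.10 also collects it at early termination.

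**Planned output for weight.** SAP 11.5 names its parameters: "Vital signs (pulse rate, blood pressure, respiration rate, and temperature) will be measured at Screening". For these, "Summary table of actual values and changes from baseline by visit for each vital sign parameter will be provided by treatment groups". Weight gets a sentence of its own: "Weight collected at Day 1 and Week 13 will be listed with vital signs".

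**Reasons in the protocol to look at weight.** In the 28-day dog study at 100 mg/kg, "BPN14770 caused inappetance and weight loss and in female dogs an approximately 30 msec increase in QTc with a concomitant increase in heart rate" (Protocol 4.3.1). The stated dog NOAEL is 30 mg/kg. In the multiple-dose study, the drug-related events in the 75 mg once-daily group of young subjects included "decreased appetite (reported by 3 of 6 subjects" (Protocol 4.3.2.2).

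**QTc.** SAP 11.6 plans by-visit and change-from-baseline tables for each ECG parameter, QTc included. It adds a count of subjects "with QTcF values (at pre-treatment and then at any time post-first dose) in the following ranges will be provided", the ranges being up to 450, above 450 to 480, above 480 to 500, and above 500 msec.

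**The concern.** Weight is measured before dosing and at the end of treatment, yet the plan produces no mean change, no spread and no arm difference for it. It also gives no count of subjects who lose a material share of their weight. To see a dose-related effect in the measured weights, someone would have to read a listing of about 255 subjects.

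This matters for two reasons. The multiple-dose study lasted 8 days, whereas this trial doses for 13 weeks, in subjects aged 55 to 85 who may enter at just above 48 kg. And SAP 3.1 and 8.3 say the results will be used to choose the Phase 3 dose, while Protocol 4.2 expects exposure at 25 mg to be 3- to 4-fold that at 10 mg. A weight effect that grows with dose is tolerability evidence for that choice.

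The QTcF categories have a smaller gap of the same kind. They count subjects by the level reached, not by how far they moved from baseline.

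**Working it through.** The plan states no figure for weight or QTc change, so there is nothing to reproduce. The check is first a reading of the planned outputs, then an illustration of what the missing table could show.

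**1. Is weight change summarised anywhere?**
- SAP 11.5: the by-arm change table covers vital-sign parameters; weight is not in that list and is assigned to a listing.
- SAP 7.2: BMI is summarised at baseline only.
- SAP 11.7: physical examination data are listed only.
- Protocol 11.5: change summaries are required for vital signs, ECG and laboratory tests; weight is not named.
- SAP 11.3: adverse events are tabulated by arm, so weight loss or decreased appetite appears if an investigator reports it.

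No by-arm summary of measured weight change is planned.

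**2. What would a by-arm weight table show?** Inputs: n = 80 per arm (SAP 3.4). The SD of 13-week weight change is an assumption, because the documents give none.

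SE of an arm difference = SD × √(2/80). 95% half-width = 1.96 × SE. Power for a 1 kg difference, two-sided 0.05 = Φ(1/SE − 1.96).

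| Assumed SD (kg) | SE (kg) | 95% half-width (kg) | Power for 1 kg |
|---|---|---|---|
| 2 | 0.316 | 0.62 | Φ(1.20) = 0.885 |
| 3 | 0.474 | 0.93 | Φ(0.15) = 0.559 |
| 4 | 0.632 | 1.24 | Φ(−0.38) = 0.352 |

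A t-based calculation gives 0.882, 0.554 and 0.349. Power is therefore about 88% at an SD of 2 kg and about 56% at 3 kg.

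**3. Would a QTc shift be seen?** SAP 11.6 plans the change-from-baseline table. SAP 6.1 presents summary tables by treatment group, with n, mean, SD, median, minimum and maximum. With 80 per arm and assumed SDs of QTc change of 15, 20, 25 and 30 msec, SE = SD × √(2/80) = 2.4, 3.2, 4.0 and 4.7 msec. A 30 msec difference between arms is then 30/2.37 = 12.6 SEs at the smallest SD and 30/4.74 = 6.3 at the largest. A shift of that size would be plain.

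**4. What do the absolute QTcF ranges miss?** A subject who goes from 400 to 445 msec rises 45 msec and stays in the lowest range. From 410 msec, a rise of 450 − 410 = 40 msec also stays there. The by-visit maximum in the change table shows the largest single rise in an arm, but not how many subjects had a large one.

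**The case against.** **On weight.** The SAP breaks no commitment: weight is not among the safety endpoints in Protocol 4.4.3 or SAP 4.3, and Protocol 11.5 promises no summary of it. Nothing is lost, since every weight is collected and listed and a table could be made later. The background is also weaker than it may look. Protocol 4.3.1 names other dog findings at 100 mg/kg as well, including a 10 bpm heart rate increase and ALT and liver changes. The appetite reports came from young subjects on a regimen that no arm of this trial uses. In the elderly twice-daily cohorts, the events reported in 2 or more subjects of a dose group did not include appetite or weight loss. Adverse event tables by arm give a partial view, and Protocol 11.5 adds Fisher's exact tests against placebo.

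All of this is correct, and it limits the seriousness of the point. It does not remove it. Adverse event tables depend on reporting and cannot estimate a mean shift, and a table made after unblinding carries less weight than one specified beforehand.

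**On QTc.** A reader might infer from the absolute ranges that a QTc increase of the size seen in dogs has no by-arm table. The documents do not support that: SAP 11.6 with SAP 6.1 provides one. The dog finding is stated as an approximate increase, for which a table of change from baseline is a suitable display. What remains is the missing count by size of increase, and an ambiguity: the change table says QTc without naming the correction, while the categories use QTcF.

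**Conclusion.** The weight gap stands. Followed as written, the SAP yields no between-arm estimate of weight change, although weight is measured at Baseline and at Week 13 or early termination and the protocol reports weight loss in dogs above the NOAEL. The data would support an estimate to within about 0.6 to 0.9 kg if the SD is 2 to 3 kg. That SD is an assumption. It would be too strong to say that a 1 kg difference is detectable in general: this is fair at 2 kg (about 88% power) but not at 3 kg (about 56%). The case rests on having an estimate at all, not on reaching significance.

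It would also be too strong to call weight loss invisible, since reported events are tabulated by arm.

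The QTc point is secondary and minor: a mean shift would be seen, and only the count of subjects by size of QTcF increase is missing. Neither point affects the primary analysis, the error rate or the sample size.

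**What to change.** **SAP 11.5.** Replace the listing-only sentence with a by-arm summary of weight and of change from baseline to Week 13 or early termination (n, mean, SD, median, minimum, maximum). Add the number and percentage of subjects whose loss exceeds a percentage cut-off that the sponsor sets before unblinding. State how early-termination weights enter the table, because SAP 6.4 assigns those visits for the efficacy analysis only. Keep the listing.

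**SAP 11.6 (minor).** Beside the absolute ranges, add the number and percentage of subjects by arm according to their largest post-dose QTcF increase from baseline, for example above 30 msec, the size named in Protocol 4.3.1. Name the QT correction used in the change-from-baseline table.

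**Cost.** Two descriptive tables from data already collected. No added visits or procedures, and no change to efficacy inference.
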